12.5 Stopping Rules

If ≥ 2 patients experience DLTs during the safety lead-in, then the dose of ibrutinib will be reduced as follows:

- Level -1 840 mg/d x 2 weeks; if ≥ 2 of 6 DLTs are observed at Level -1, dosing will be de-escalated to Level -2
- Level -2 560 mg/d x 2 weeks

If ≥ 2 patients experience DLTs at Level -2, then the study will be terminated for lack of safety.

Toxicity is continuously monitored for all patients.

12.5.1 Non-hematological Toxicity and plans for data and safety monitoring

Early stopping of the Phase II phase of the trial will be based on unacceptable non-hematological toxicity. Approximately less than 15% of patients are expected to

experience grade 3 and up toxicity and a non-hematological toxicity rate of 30% or more would definitely be unacceptable. Based on the sequential probability ratio test (SPRT) with 80% power and a 0.05 significance level, the study will be halted if 4 of the first 4, or 5 of the first 9, or 6 of the first 14, or 7 of the first 18, or 8 of the first 23, or if the 9th non-hematological toxicity is observed before the last patient has completed the trial. Accrual will be stopped and the event will be reviewed by the Data Safety and Monitoring Board if a grade 5 non-hematological toxicity is observed.

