Exploratory Objectives	
• To examine Btk expression in prostate tumor cells and tumor-infiltrating B cells.• To determine the impact of neoadjuvant ibrutinib on PD-L1 expression in prostate cancer cells and tumor-infiltrating lymphocytes (TILs).• To determine the effects of neoadjuvant ibrutinib on T and B cell repertoire within the tumor and blood.

Study Design	
This is a phase 2 study of neoadjuvant ibrutinib in men with localized prostate cancer undergoing RP as their initial locally directed therapy with curative intent. In the safety lead-in phase, a cohort of 6 patients will be treated with ibrutinib 840 mg/d x 4 weeks to assess safety and adverse events (AEs). If no more than 2 out of 6 patients experience dose limiting toxicities (DLT), the study will continue accruing. DLTs will be assessed during the safety lead-in phase only, during treatment with ibrutinib and the period prior to RP. To assess the immune response following neoadjuvant treatment, tissue from RP specimen will be compared to tissue from core biopsy specimen obtained prior to treatment, with each subject serving as his own control. Immune infiltration will also be compared to a reference cohort of 12 patients who had undergone RP, matched to the study population using the UCSF CAPRA-S score.

Number of patients	
Three patients were enrolled at UCSF in an 840 mg/d x 2 weeks cohort; no DLTs occurred. At WUSM, a safety lead-in of 6 patients will be accrued at the 840 mg/d x 4 week dose level. In the event that no DLTs are encountered, an additional 18 patients will be enrolled for a total of 24 patients at the 840 mg/d x 4 week dose level. A full safety assessment will be carried out after the first 10 patients have completed the phase 2 study (6 in the safety lead-in + 4), and accrual will be suspended if 3 or more of these 10 patients experience grade 3 or 4 treatment-related toxicity.
 
If RP is delayed over 12 days after the last dose of ibrutinib therapy (i.e. from scheduling delay of RP), a replacement patient will be accrued. The maximum number of allowed replacement patients is 4 (see Section 12.4).

Duration of Therapy	All patients will receive ibrutinib for 4 weeks prior to RP. RP will be performed 7 to 12 days after the last dose of ibrutinib.
Duration of Follow up	All patients will be followed for 4 weeks after RP.

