3 STUDY DESIGN

3.1 Characteristics

This is a single center phase 2 open label study starting with a safety lead-in ibrutinib administered as neoadjuvant therapy in patients with localized prostate cancer. We believe that the dose of ibrutinib 840mg x 4 weeks will be well tolerated in patients with localized prostate cancer based on current trial data on ibrutinib but to ensure safety, we will start with a safety run-in. Previously at UCSF, 3 patients were enrolled to the 840 mg/d x 2 weeks dose level. No DLTs were observed. Beginning at WUSM, patients will be enrolled at the dose level of 840 mg/d x 4 weeks. If there are fewer than 2 DLTs, the Phase II dose expansion study will open and enroll up to an additional 18 patients to be treated with ibrutinib 840mg PO daily for 4 weeks.

If there are ≥ 2 DLTs in the safety lead-in, dosing will be de-escalated as follows:

- Level -1: 840 mg/d x 2 weeks, followed by de-escalation if ≥ 2 DLTs to Level -2
- Level -2: 560 mg/d x 2 weeks

In each enrolled patient, neoadjuvant ibrutinib therapy will be followed by radical prostatectomy (RP) performed 7 to 12 days after the last dose of ibrutinib. Pre-treatment and RP tissue will be evaluated for immunologic characterization, Btk expression and pathologic response. The proportion of patients achieving $\geq 50\%$ PSA decline will be assessed. Serum will also be obtained to characterize circulating immune response. All patients will be followed clinically for 4 weeks after RP to monitor for adverse events.

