3.2 Number of Subjects

The safety lead-in part requires 6 patients at the 840 mg/d x 4 weeks dose level. The phase II study will require a total of 24 patients (6 in the safety lead-in plus an additional 18). A sequential stopping rule is in place during Phase II (see Section 12.5).

If RP is delayed to over 12 days after the last dose of ibrutinib therapy (i.e. from scheduling delay of RP), a replacement patient will be accrued. The maximum number of allowed replacement patients is 4 (see Section 12.4).

To date, 3 patients have been enrolled and treated at UCSF (PI: [name]) in Phase I/Cohort I (840 mg x 2 weeks) with no DLTs noted to date.

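### Section 12.5.1 credits the toxicity boundary with 80% power at 0.05; ended at the planned 24 patients, the boundary alone halts with probability 0.43 at a true 30% rate

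*Combined protocol and SAP*

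**What the plan says.** Section 12.5.1 names its purpose: "Early stopping of the Phase II phase of the trial will be based on unacceptable non-hematological toxicity". It gives two reference rates. For the acceptable side, "Approximately less than 15% of patients are expected to" have a toxicity of grade 3 or higher. For the other side, "a non-hematological toxicity rate of 30% or more would definitely be unacceptable".

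It then presents the rule: "Based on the sequential probability ratio test (SPRT) with 80% power and a 0.05 significance level, the study will be halted" if toxicities reach 4 of the first 4, 5 of the first 9, 6 of the first 14, 7 of the first 18, 8 of the first 23, or if a 9th occurs before the last patient completes. It gives no acceptance boundary, no adjustment for a maximum sample size and no other operating characteristics.

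On size, Section 3.2 says "The phase II study will require a total of 24 patients (6 in the safety lead-in plus an additional 18" and adds "A sequential stopping rule is in place during Phase II (see Section 12.5". Section 3.1 uses the term differently: after the lead-in, "the Phase II dose expansion study will open and enroll up to an additional 18 patients". Section 12.4 allows up to 4 replacements for delayed surgery. Section 12.5 says toxicity is monitored continuously.

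**The concern.** An SPRT's nominal error rates hold when sampling continues until one of two boundaries is crossed. Here there is only an upper boundary and sampling stops at a small fixed number of patients. Many paths that would eventually have crossed never get the chance, so power must fall below nominal. The plan quotes the nominal figure without saying so.

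Safety is a primary objective, and this is the formal halting rule for phase II. A reader of Section 12.5.1 will take a trial that runs to the end without a halt as good evidence against a 30% toxicity rate. If the true chance of a halt at 30% is about half the figure given, that reassurance is much weaker than it looks.

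**Working it through.** **Inputs.** p0 = 0.15, p1 = 0.30, nominal α = 0.05 and power 0.80, and the cut-offs (all Section 12.5.1). N = 24 (Section 3.2), or 28 with 4 replacements (Section 12.4). N = 18 if only the expansion counts (Section 3.1), or 22 with replacements. Assumptions: at most one counted event of grade 3 or higher per patient, independent patients, and a check after each patient.

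**1. Reproduce the cut-offs.** Wald's upper line for k events in n patients is

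k·ln(p1/p0) − (n − k)·ln[(1 − p0)/(1 − p1)] = ln[power/α].

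With the numbers in: k·ln 2 − (n − k)·ln(0.85/0.70) = ln(0.80/0.05) = ln 16, that is, 0.6931k − 0.1942(n − k) = 2.7726. Solving for n:

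| Events k | n on the line | Rounded up | Printed |
|---|---|---|---|
| 4 | 4.00 | 4 | 4 |
| 5 | 8.57 | 9 | 9 |
| 6 | 13.14 | 14 | 14 |
| 7 | 17.71 | 18 | 18 |
| 8 | 22.28 | 23 | 23 |

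The cut-offs are right for these inputs. So 0.80 and 0.05 went into the formula; they are not properties computed for the finished rule.

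**2. Where 80% and 0.05 do hold.** The open-ended SPRT with both boundaries, run to n = 500, crosses the upper boundary with probability 0.82 at 30% and 0.040 at 15%, close to nominal.

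**3. The printed rule, ended at N.** Exact recursion: let f(n, k) be the probability of k events after n patients with no halt so far. Then f(n, k) = (1 − p)·f(n−1, k) + p·f(n−1, k−1), and any mass that reaches the lowest cut-off still active is moved to the halt total.

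| Patients counted | P(halt) at 30% | P(halt) at 15% |
|---|---|---|
| 18 | 0.3172 | 0.0188 |
| 22 | 0.3880 | 0.0225 |
| 24 | 0.4265 | 0.0253 |
| 28 | 0.5242 | 0.0315 |

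Checking only at the listed counts also gives 0.4265 at N = 24. The 9th-event clause adds nothing there, because 9 events by patient 24 require at least 8 by patient 23. A simulation of 400,000 runs agrees (0.4259 and 0.0249). With 24 patients, P(halt) is 0.789 at a true rate of 40% and 0.816 at 41%.

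**4. How many patients 80% would need.** Continuing the same line upward, rounded up and with no acceptance boundary, P(halt) at 30% is 0.7956 at 57 patients and 0.8029 at 58.

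**5. Could other cut-offs deliver it?** By the Neyman–Pearson lemma, no rule on n patients beats the randomized binomial test. For n = 24, rejecting at 8 or more events has level 0.0199 and power 0.4353; at 7 or more, 0.0572 and 0.6114. Reaching exactly 0.05 requires randomizing at 7 with probability (0.05 − 0.0199)/(0.0572 − 0.0199) = 0.807. Power is then 0.4353 + 0.807 × (0.6114 − 0.4353) = 0.577. The limit is 0.486 for n = 18 and 0.638 for n = 28.

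**The case against.** **The 80% may only describe the derivation.** Step 1 supports this as an account of where the figure came from. But the section offers no other operating characteristic, so a reader has no way to know that the rule as run behaves differently.

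**More patients might be counted.** With two de-escalations, Section 12.3 allows 12 more patients. On an all-treated count of 36 the printed rule halts with probability 0.80 at 30%, and at 40 with 0.89. That reading is strained, since Section 12.5.1 confines the rule to phase II. It also fails on the other half of the label: the halting probability at 15% is then 0.087 and 0.14, and the limit for any rule at 0.05 is 0.71 and 0.75. Adding the three UCSF patients to the 24 gives 27 (0.49), or 31 with replacements (0.64). No count delivers 80% and 0.05 together.

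**Events or patients?** The halting clause gives no grade, and its last part counts toxicities. The phrasing by first n patients supports a patient count, but the assumption should be stated next to any probability that is inserted.

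**Other safeguards act earlier.** This is true: there is the lead-in DLT rule, review after a grade 5 event, and the Abstract's rule that "accrual will be suspended if 3 or more of these 10 patients experience grade 3 or 4 treatment-related toxicity". If one common event and rate is assumed for all rules, which their definitions do not support exactly, adding the 3-of-10 rule gives 0.67 at 30% and 0.18 at 15%; adding the lead-in rule as well gives 0.73 and 0.27. These rules suspend or de-escalate and do not trigger this halt, Section 12.5.1 does not credit them, and the total is still below 0.80. What stands is that the 57% describes this boundary alone, not the trial's whole protection.

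**Conclusion.** The power statement is wrong as written. The cut-offs are sound. With 24 patients the boundary halts with probability 0.43 at a true 30% rate, against the 0.80 stated, and 0.025 at 15%, against 0.05. It stays silent with probability 1 − 0.43 = 0.57 at the rate the plan calls definitely unacceptable. Counting 18, 22 or 28 patients changes the size (0.32 to 0.52 at 30%) but not the conclusion, and the limit in step 5 shows that 80% at 0.05 is out of reach at the planned size whatever cut-offs are used. The figures rest on one counted event per patient, independent patients and this boundary acting alone.

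**What to change.** In Section 12.5.1, first state whether the six lead-in patients count toward the boundary, reconciling Sections 3.1 and 3.2, and confirm that each patient counts at most once and at which grade. Then replace the power and significance claim with the properties of the truncated rule. If all 24 count, for example:

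> The cut-offs are derived from an SPRT of 15% versus 30%. With at most 24 patients, each counted once, the probability of halting under this rule alone is 0.43 at a true rate of 30% and 0.025 at 15% (0.52 and 0.03 with all 4 replacements).

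If only the 18 expansion patients count, the figures are 0.32 and 0.02 (0.39 and 0.02 with replacements).

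As a separate matter of placement, list the Abstract's 3-of-10 suspension in Section 12.5 with its own event definition, so that all safety rules in force appear together. The verdict does not depend on this.

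The cost is wording only. The stated power becomes less favourable; no patients are added, and no cut-off or clinical rule changes.

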12.6 Analyses Plans

12.6.1 Analysis Population

All patients who receive a dose of ibrutinib will be analyzed for safety and efficacy. Subjects who discontinue from study participation prior to receiving any dose of study therapy may be replaced after discussion with the Study Monitor. Subjects who have received any dose of study therapy will not be replaced.

Demographic and baseline characteristics will be summarized by each cohort and overall. In general, frequency distribution and percentage will be used to summarize categorical measurements, while mean with standard deviation and median with range will be used to describe symmetric and skewed continuous measurements, respectively. Univariate analysis among variables will be assessed using the two-sample t-test, Wilcoxon-rank-sum test, Chi-square test, as appropriate.

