12.3 Sample Size and Power Estimate

For this phase 2 study, the primary endpoint is the change of B cells between the pre-treatment biopsy and post-treatment RP specimen. Each patient's response to neoadjuvant ibrutinib will be a binary classification. Patients will be considered to have a

“positive” response if there is >2 fold decrease in the number of B cells, or considered to have a “negative” response if there is <2 fold decrease in the number of B cells. The accrual of 18 patients to the phase 2 trial and incorporation of 6 patients who received ibrutinib at MTD in the safety lead-in (a total of 24 evaluable subjects) will be sufficient to determine whether 20% or more of the cohort achieves this 2 fold decrease in B cells, compared to a null response of 5% or less of a reference group of patients who underwent RP without neoadjuvant treatment. This comparison has a power of 0.818 at a significance level of 0.044 based on a one-sided binomial exact test. If 4 more evaluable patients show a “positive” response, the treatment achieves the expected “response” rate of 20%.

The safety-run in will require 6 patients (with a potential for 6-12 more if dose de-escalation is required). The Phase II study will require a total of 24 patients on MTD and thus 18 additionally enrolled patients besides the 6 on MTD during the safety lead-in.

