12.6.2.2 Intratumoral Immune Infiltration

For all subjects, immune cell subsets and localization will be summarized by changes from baseline to after treatment. Patients will be considered to have a positive response if there is ≥ 2 fold decrease in the number of B cells, or considered to have a negative response if there is < 2 fold decrease in the number of B cells. The proportion of patients who have “positive” responses will be reported, with 95% confidence intervals. Descriptive statistics will be used to describe pre-treatment biopsy immune infiltration, post-treatment RP immune infiltration, and immune infiltration of reference RP tissue.

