12.9 UCSF's Data

Data from the first three patients enrolled at UCSF will be shared with Washington University under a Data Use Agreement and analyzed under the auspices of this study.

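### The plan gives two efficacy populations for the primary B-cell endpoint: every dosed man (12.4, 12.6.1, 12.6.2.2) or 24 men at one dose level (12.3), and does not reconcile them

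*Combined protocol and SAP*

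**What the plan says.** **Every dosed man.** Section 12.6.1 reads "All patients who receive a dose of ibrutinib will be analyzed for safety and efficacy", and 12.4 repeats the rule. Section 12.6.2.2, the primary tissue analysis, begins "For all subjects, immune cell subsets and localization will be summarized by changes from baseline to after treatment" and then reports one responder proportion with a 95% confidence interval. None of the three limits the set by dose or duration.

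**One dose level.** Section 12.3 says "The Phase II study will require a total of 24 patients on MTD", made up of 6 lead-in men and 18 more, and calls them "a total of 24 evaluable subjects". Section 2.2.1 makes infiltration the primary endpoint of the phase II part, separate from the safety endpoint of the lead-in. Section 3.2 also counts phase II as 6 plus 18.

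**Men outside the 24.** Three UCSF men received 840 mg/d for 2 weeks (3.1, 3.2). They are registered in the study database (4.4), and 12.9 says "Data from the first three patients enrolled at UCSF will be shared with Washington University under a Data Use Agreement and analyzed" as part of this study, without saying whether pooled or apart. Section 12.3 also allows for 6 to 12 further men if the dose is de-escalated.

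**Where regimens are separated.** Baseline data are summarized by cohort and overall (12.6.1), pT0 is limited to phase 2 subjects (12.6.3.2), and sequencing is split by dose level (12.6.4.3). The primary infiltration analysis in 12.6.2.2 carries no such limit.

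**The concern.** The two descriptions give different denominators for the same primary result. Leaving aside replacements for delayed surgery, the set is 24 under 12.3. Under a literal 12.6.1 it is 27 with no de-escalation, 33 after one step and 39 after two. Two analysts could follow different sections and report different primary proportions, and the choice could be made after the data are seen.

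If de-escalation occurs, men from a level the trial has just rejected would count toward the result for the level taken forward. If it does not, the estimate for the 4-week regimen would still include three men who had half the course.

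**Working it through.** **Inputs.** From 12.3: null rate 5% ("compared to a null response of 5% or less of a reference group"), alternative 20% ("whether 20% or more of the cohort achieves this 2 fold decrease in B cells"), N = 24, and success at 4 responders (its wording is read as 4 or more). From 3.1: 3 UCSF men. From 12.3: 6 or 12 extra men on de-escalation. Assumed, because the documents give no figure: the response rate of men outside the 24.

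**Step 1: the plan's own figures.** Section 12.3 states "This comparison has a power of 0.818 at a significance level of 0.044 based on a one-sided binomial exact test". For an exact test with cutoff 4,

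P(X ≥ 4) = 1 − Σ C(n,x) p^x (1−p)^(n−x), x = 0 to 3.

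- n = 24, p = 0.05: 1 − (0.29199 + 0.36883 + 0.22324 + 0.08616) = 0.0298
- n = 24, p = 0.20: 1 − (0.00472 + 0.02833 + 0.08146 + 0.14934) = 0.736

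So the rule on 24 men has alpha 0.030 and power 0.736. A cutoff of 3 gives 0.116 and 0.885; a cutoff of 5 gives 0.006 and 0.540. No cutoff at n = 24 gives 0.044 and 0.818. A search over n = 10 to 59 and cutoffs 1 to 11 finds one match: n = 27, cutoff 4 (0.0437, 0.8177). A one-sided normal approximation at n = 24 with alpha set to 0.044 also gives power 0.818, but that is not the exact test named.

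**Step 2: enlarged set, all men at the null 5%, cutoff kept at 4.**

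| Set | n | P(4 or more) |
|---|---|---|
| Selected level only | 24 | 0.030 |
| + UCSF three | 24 + 3 = 27 | 0.044 |
| + 6 abandoned-level | 24 + 6 = 30 | 0.061 |
| + 6 and UCSF three | 24 + 6 + 3 = 33 | 0.081 |
| + 12 abandoned-level | 24 + 12 = 36 | 0.104 |
| + 12 and UCSF three | 24 + 12 + 3 = 39 | 0.129 |

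**Step 3: selected level at 5%, abandoned levels at a higher rate (assumption), UCSF men left out.** With k abandoned-level men responding at rate q, P(success) = Σ P(A = a)·P(B = b) over a + b ≥ 4, where A ~ Bin(24, 0.05) and B ~ Bin(k, q).

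| q | k = 6 | k = 12 |
|---|---|---|
| 5% | 0.061 | 0.104 |
| 10% | 0.10 | 0.22 |
| 20% | 0.21 | 0.49 |

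With the cutoff raised to 5, the q = 5% row becomes 0.016 and 0.032, and the q = 20% row becomes 0.082 and 0.286.

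**Step 4: no de-escalation, 24 men at 20% plus the UCSF three.** With cutoff 4, the chance of success is 0.758, 0.779 or 0.818 if the UCSF men respond at 5%, 10% or 20%. The comparator is 0.736 on the 24 alone. Added men cannot reduce the number of responders, so with a fixed cutoff the chance of success can only rise.

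**The case against.** The strongest reply is that the plan already limits the test. Section 12.3 contains the only test of this endpoint and defines it for 24 men at one level. Section 2.2.1 assigns infiltration to phase II, and 3.2 places the UCSF men in an earlier cohort. Section 12.6.2.2 gives a proportion and an interval and names no test. This stands as far as it goes: a reader might infer that the plan pools regimens in the 12.3 test, but no section says so. It does not remove the conflict, because 12.4 and 12.6.1 expressly extend efficacy to every dosed man and 12.6.2.2 reports the proportion for all subjects.

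A second reply is that the larger error rates stack conditions: one or two de-escalations, a cutoff left at 4 on a larger set, and for the highest figures abandoned levels responding at 20% while the selected level stays at 5%. That is fair. An exact test held to 12.3's significance level would move the cutoff to 5 at n = 30 or 36. With every man at 5% that restores control; with abandoned-level men at 20% it does not (0.082 and 0.286).

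A third reply concerns the UCSF men. A reader might infer that adding them lowers power from 0.818 to 0.758. It does not: 0.818 is not the exact power on 24 men, and against the correct 0.736 the chance of success rises. Alpha with them included stays below 0.05. Nor can the match at n = 27 be read as proof that they were counted in the design; 24 + 3 is 27, but the documents never state that number.

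**Conclusion.** The conflict is real and should be resolved before analysis. It lies between two stated rules and is more than a missing detail.

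Its size depends on events. Without de-escalation, the literal reading gives a proportion and interval that mix 4-week and 2-week treatment, with no loss of power and a false-positive rate of 0.044. With de-escalation and an unchanged cutoff, the rate under a uniform 5% is 0.061 to 0.129, against 0.030 for the 24 alone and 0.044 stated. With abandoned-level men at 10% to 20% it is 0.10 to 0.21 for one abandoned level and 0.22 to 0.49 for two. Those ranges rest on assumed response rates.

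Separately, the figures in 12.3 do not belong to the exact test on the 24 men that 12.3 describes.

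**What to change.** 1. In 12.4 and 12.6.1, keep all dosed men for safety, tabulated by dose level.
2. Define the primary efficacy set for 12.3, 12.6.2.2 and 12.6.3 as the men treated in this trial's cohort at the dose level carried into phase II (6 plus 18).
3. Report the UCSF three and any abandoned-level men separately and descriptively. State in advance how the UCSF three are handled if Level -1 is carried forward, since that is the regimen they received.
4. Restate 12.3 for that set: n = 24, 4 or more responders, exact alpha 0.030, power 0.736.

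The cost is wording. Up to 15 men (12 + 3) are shown descriptively and do not enter the primary proportion, and the stated power is less favourable. No dose or clinical rule changes.
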